10.7 Justification of Surrogate Consent

According to the Belmont Report, respect for persons incorporates at least two ethical convictions; first, that individuals should be treated as autonomous agents, and second, that persons with diminished autonomy are entitled to protection. One method that serves to protect patients is restrictions on the participation of patients in research that presents greater than minimal risk. Commentators and research ethics commissions have held the view that it is permissible to include incapable participants in greater than minimal risk research as long as there is the potential for beneficial effects and that the research presents a balance of risks and expected direct benefits similar to that available in the clinical setting.⁴⁷ Several U.S. task forces have deemed it permissible to include incapable participants in research. For example, the American College of Physicians’ document allows surrogates to consent to research involving incapable participants only “if the net additional risks of participation are not substantially greater than the risks of standard treatment”.⁴⁸ Finally, NBAC stated that an IRB may approve a protocol that presents greater than minimal risk but offers the prospect of direct medical benefits to the participant, provided that “the potential subject’s LAR gives permission...”.⁴⁶

Consistent with the above ethical sensibilities regarding the participation of decisionally incapable participant in research and the previous assessment of risks and benefits in the previous section, the present trial presents a balance of risks and potential direct benefits that is similar to that available in the clinical setting.

10.8 Additional Safeguards for Vulnerable Participants

The present research will involve participants who might be vulnerable to coercion or undue influence. As required in 45CFR46.111(b), we recommend that sites utilize additional safeguards to protect the rights and welfare of these participants. Such safeguards might include but are not limited to: a) assessment of the potential participant’s capacity to provide informed consent, and b) the availability of the LAR to monitor the participant’s subsequent participation and withdrawal from the study. The specific nature of the additional safeguards will be left to the discretion of the central IRB, in conjunction with the sites.

10.9 Confidentiality

Federal regulations at 45 CFR 46 111 (a) (7) requires that when appropriate, there are adequate provisions to protect the privacy of participants and to maintain the confidentiality of data. At no time during the course of this study, its analysis, or its publication will patient identities be revealed in any manner. The minimum necessary data containing patient or provider identities will be collected. All patients will be assigned a unique study ID number for tracking. All data collected for this study will be entered directly into a secure online database. All data will be maintained in the secure online database until the time of study publication. At the time of publication, a de-identified version of the database will be generated. Further, tools within the secure online database will be used so that only the coordinating center and investigators from the enrolling site will have access to data from participants enrolled at that site.

11. ADVERSE EVENTS

Assuring patient safety is an essential component of this protocol. Hydroxychloroquine has been approved by the Food and Drug Administration and used in clinical practice for decades with an established safety profile. Use of hydroxychloroquine for the treatment of acute respiratory infection due to COVID-19, however, raises unique safety considerations. This protocol addresses these considerations through:

1. Exclusion criteria designed to prevent enrollment of patients likely to experience adverse events with receipt of hydroxychloroquine;
2. Proactive education of treating clinicians regarding medication interactions relevant to use of hydroxychloroquine in the inpatient setting;
3. On-study monitoring of co-interventions (e.g., medications) and patient characteristics (e.g., EKG) to intervene before adverse events occur;
4. Systematic collection of safety outcomes relevant to use of hydroxychloroquine in this setting;
5. Structured reporting of adverse events

11.1 Adverse Event Definitions

Adverse Event: Any untoward medical occurrence associated with the use of a drug or a study procedure, whether or not considered drug related.

Serious Adverse Event: A serious adverse event is any adverse event that results in one of the outcomes listed in section 11.3 below.

Adverse Reaction: An adverse reaction means any adverse event caused by a study intervention. An adverse reaction is a subset of all suspected adverse events where there is a reason to conclude that the study intervention caused the event.

Suspected Adverse Reaction: Any adverse event for which there is a reasonable possibility that the study procedures caused the adverse event. Reasonable possibility means there is evidence to suggest a

causal relationship between the study procedures and the adverse event. A suspected adverse reaction implies a lesser degree of certainty about causality than adverse reaction.

Suspected Unexpected Serious Adverse Reaction (SUSAR): An adverse reaction that is both unexpected (not consistent with risks outlined in the study protocol or investigator brochure), serious, and meets the definition of a suspected adverse reaction.

11.2 Safety Monitoring

Assuring patient safety is an essential component of this protocol. Each participating investigator has primary responsibility for the safety of the individual participants under his or her care. The Investigators will determine daily if any adverse events occur during the period from enrollment through **study day 7** (48 hours after completion of the study drug) or hospital discharge, whichever occurs first and will determine if such adverse events are reportable. Thereafter, adverse events are not required to be reported unless the investigator feels the adverse event was related to study drug or study procedures.

The following adverse events will be considered reportable and thus collected in the adverse event case report forms:

- Serious adverse events
- Non-serious adverse events that are considered by the investigator to be related to study procedures or of uncertain relationship (Appendix C)
- Events leading to permanent discontinuation of study drug

Study-specific clinical outcomes (Primary, Secondary and Safety Outcomes and Assessments During the Study), including serious outcomes such as organ failures and death, are systematically recorded in the case report forms and are exempt from adverse event reporting unless the investigator deems the event to be related to the administration of study drug or the conduct of study procedures (or of uncertain relationship) as outlined in Appendix C.

After randomization, adverse events must be evaluated by the investigator. If the adverse event is judged to be reportable, as outlined above, then the investigator will report to the CCC their assessment of the potential relatedness of each adverse event to the study drug or protocol procedure via electronic data entry. Investigators will assess if there is a reasonable possibility that the study procedure caused the event, based on the criteria outlined in Appendix C. Investigators will also consider if the event is unexpected. Unexpected adverse events are events not listed in the study protocol and the investigator brochure for Hydroxychloroquine. Investigators will also determine if adverse events are unanticipated given the patient's clinical course, previous medical conditions, and concomitant medications.

If a patient's treatment is discontinued as a result of an adverse event, study site personnel must also report the circumstances and data leading to discontinuation of treatment in the adverse event case report forms.

11.3 Serious Adverse Events

Serious adverse event collection begins after randomization and study procedures have been initiated. If a patient experiences a serious adverse event after consent, but prior to randomization or starting study procedures, the event will NOT be collected. Study site personnel must alert the CCC of any **serious and**

study procedure related adverse event within 24 hours of investigator awareness of the event. Alerts issued via telephone are to be immediately followed with official notification on the adverse event case report form. See Appendix C for reporting timelines for serious, unexpected, study related events (SAEs) and serious, unexpected suspected adverse reactions (SUSARs)

As per the FDA and NIH definitions, a serious adverse event is any adverse event that results in one of the following outcomes:

- Death
- A life-threatening experience (that is, immediate risk of dying)
- Prolonged inpatient hospitalization or re-hospitalization

As per <http://www.fda.gov/Safety/MedWatch/HowToReport/ucm053087.htm>: Report if admission to the hospital or prolongation of hospitalization was a result of the adverse event. Emergency room visits that do not result in admission to the hospital should be evaluated for one of the other serious outcomes (e.g., life-threatening; required intervention to prevent permanent impairment or damage; other serious medically important event).

- Persistent or significant disability/incapacity

As per <http://www.fda.gov/Safety/MedWatch/HowToReport/ucm053087.htm>: Report if the adverse event resulted in a substantial disruption of a person's ability to conduct normal life functions, i.e., the adverse event resulted in a significant, persistent or permanent change, impairment, damage or disruption in the patient's body function/structure, physical activities and/or quality of life.

Reportable serious adverse events that may not result in death, be life-threatening, or require hospitalization may be considered serious adverse events when, based upon appropriate medical judgment, they may jeopardize the patient and may require medical or surgical intervention to prevent one of the outcomes listed in this definition.

Serious adverse events will be collected during the first **7 study days** or until hospital discharge, whichever occurs first, regardless of the investigator's opinion of causation.

12. Data and Safety Monitoring Board (DSMB)

The principal role of the DSMB is to assure the safety of participants in the trial. They will regularly monitor data from this trial, review and assess the performance of its operations, and make recommendations to the steering committee and NHLBI with respect to:

- Review of adverse events
- Interim results of the study for evidence of efficacy or adverse events
- Possible early termination of the trial because of new external information, early attainment of study objectives, safety concerns, or inadequate performance
- Possible modifications in the clinical trial protocol
- Performance of individual centers

The NHLBI PETAL Network DSMB is appointed by the Director of the NHLBI and makes recommendations to the Director. The DSMB reviews all protocols for safety following review by an

independent NHLBI Protocol Review Committee. The DSMB will consist of members with expertise in acute lung injury, emergency medicine, biostatistics, ethics, and clinical trials. An NHLBI staff member not associated with PETAL will serve as Executive Secretary. Appointment of all members is contingent upon the absence of any conflicts of interest. All the members of the DSMB are voting members. The Principal Investigator and the Medical Monitor of the CCC will be responsible for the preparation of all DSMB and adverse event reports and may review unblinded data. The DSMB will develop a charter and review the protocol and sample consent form during its first meeting. Subsequent DSMB meetings will be scheduled in accordance with the DSMB Charter with the assistance of the CCC. When appropriate, conference calls may be held in place of face-to-face meetings. Recommendations to end, modify, or continue the trial will be prepared by the DSMB executive secretary for review by the NHLBI Director. Recommendations for major changes, such as stopping the trial, will be reviewed by the NHLBI Director and communicated immediately. Other recommendations will be reviewed by the NHLBI director and distributed in writing to the CCC, which will distribute to the PETAL steering committee with instructions for reporting to local IRBs when appropriate.

Details of the NHLBI policies regarding DSMBs can be found at the following URL:

<https://www.nhlbi.nih.gov/grants-and-training/policies-and-guidelines/nhlbi-policy-data-and-safety-monitoring-extramural-clinical-studies>

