4. STUDY INTERVENTIONS

4.1 Treatment of Study Participants

A summary of the trial's schedule of events is included in Appendix A.

Timing of study procedures is based on the time of randomization, which is defined as "Time 0". The primary outcome will be assessed on Study Day 15, which corresponds to 14 days (2 weeks) after randomization.

Study medications will be administered by clinical or research personnel while the patient is hospitalized. The first dose of study medications will be administered within 4 hours of randomization. In the hospital, medication delivery after the first dose will correspond to the timing of morning and evening medication delivery for the hospital/unit. If the patient is discharged prior to completion of the study medication, the patient will be discharged with the study medication packet to complete the course after discharge. At home, the patient will be instructed to take the morning dose upon awakening and the evening dose approximately 12 hours later.

On Study Days 1-5, study personnel will review patient records to confirm administration of study drug and document the number and reason for any missed doses. For patients who are discharged prior to Day 5, study personnel will obtain data on study drug adherence and safety outcomes from the patient or surrogate at via telephone follow-up scheduled at Day 8. Research personnel will also assess patients at Day 15 and Day 29; these assessments will be completed by phone if the patient has been discharged from the hospital.

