4.2 Hydroxychloroquine Group

Participants assigned to the hydroxychloroquine arm will receive hydroxychloroquine sulfate 400 mg enterally twice daily for the first two doses and then 200 mg twice daily for the subsequent eight doses ("Days 2 – 5"). This dosing regimen is a total of 10 doses over 5 days with an 800 mg load in the first 24 hours divided into two doses followed by 400 mg daily divided into two doses over the following 4 days. Medication dose packs containing all 10 doses will be provided at randomization by the investigational pharmacy.

Hydroxychloroquine is available in 200 mg oral tablets of hydroxychloroquine sulfate. Common hydroxychloroquine dosing for treatment of uncomplicated malaria is 800 mg followed by 400 mg at 6 hours, 24 hours, and 48 hours. Common initial dosing for rheumatoid arthritis is 400 mg to 600 mg daily. For this COVID-19 trial, we selected a dose of hydroxychloroquine (400 mg twice daily for the first two doses followed by 200 mg twice daily for next 8 doses) based on similar doses being well tolerated in the treatment of other conditions and *in vitro* studies suggesting that SARS-CoV-2 inhibition is achieved by a dose of 800 mg on the first day followed by 400 mg for the following 4 days.⁵ This dose and duration is comparable to the dose and duration being administered empirically to patients with COVID-19 as a part of clinical care during the current epidemic.

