6.3 Assessments following Hospital Discharge

6.3.1 Acute Care Follow-up

For participants discharged from the study hospital prior to the Day 8, Day 15 or Day 29 assessment, we will perform these assessments via telephone follow-up. The Day 8 call window will be Day 8 through 14. The Day 15 call window will be Day 15 through 22. The Day 29 call window will be Day 29 through 36. During these telephone calls, we will interview the patient, LAR, or facility staff to assess:

- Number and reason for missed doses of study drug (only for those discharged prior to completing study drug)
- Date of death (if applicable)
- ED visits, hospital readmissions, and use of supplemental oxygen after hospital discharge
- Non-laboratory safety outcomes after hospital discharge and adverse events
- Symptoms of acute respiratory infection
- COVID Ordinal Outcomes Scale

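### All-cause SAE collection closes at discharge even for patients sent home on study drug, leaving a narrow gap up to Study Day 7 for events judged unrelated

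*Protocol*

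**What the plan says.** Protocol 11.3 sets the period for collecting SAEs irrespective of cause: seven study days "or until hospital discharge, whichever occurs first". Protocol 11.2 gives the matching limit for the investigator's daily adverse event review, and its basis: Study Day 7, explained as "48 hours after completion of the study drug) or hospital discharge, whichever occurs first". After that point, "Thereafter, adverse events are not required to be reported unless the investigator feels the adverse event was related to study drug or study procedures".

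Four other places bear on this limit:

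- **Dosing after discharge.** Protocol 4.2: "This dosing regimen is a total of 10 doses over 5 days". Under 4.1, if discharge comes before the course is complete, "the patient will be discharged with the study medication packet to complete the course after discharge".
- **Seriousness criteria.** The list in 11.3 includes "Prolonged inpatient hospitalization or re-hospitalization".
- **Follow-up calls.** For discharged patients, 6.3.1 lists the content of the Day 8, 15 and 29 calls. It includes "Non-laboratory safety outcomes after hospital discharge and adverse events", and also deaths, emergency visits and readmissions. Appendix A marks adverse event monitoring on the same three days, by telephone after discharge.
- **Analysis.** SAP 7.6 reports adverse event frequencies overall and by randomized group. It says nothing about unequal observation time.

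**The concern.** The Day 7 limit is meant to cover treatment plus 48 hours. For a patient who goes home during treatment, the discharge clause closes all-cause collection while doses remain to be taken. Re-hospitalization can only happen after discharge, so by the time that criterion can be met the all-cause window has closed, and it operates only for events judged related.

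The protocol also gives sites two messages. Sections 6.3.1 and Appendix A have staff ask about adverse events up to Day 29, while 11.2 says that those not thought related need not be reported. A site that learns on the Day 8 call of an unrelated serious event on Day 5 cannot tell whether to enter it.

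Finally, the window length depends on something that happens after randomization. Discharge status separates levels 6 and 7 of the primary scale from the hospitalized levels, and time to discharge and hospital-free days are secondary outcomes in the SAP. If one arm were discharged sooner, it would be watched for all-cause SAEs for less time and would look safer for that reason alone.

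**Working it through.** **1. The plan's own figure.** Inputs: 10 doses, twice daily (4.2); drug delivery marked on Days 1 to 5 (Appendix A); Study Day 1 is the calendar day of randomization (SAP Appendix B). With two doses on Day 1, dose 10 falls on Day 5, and Day 5 + 2 days = Day 7. The stated limit reproduces. If a late randomization allows only one dose on Day 1, dose 10 falls on Day 6, and 48 hours later is Day 8.

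**2. What the discharge clause removes.** Let d be the discharge day (counted as covered) and f the doses given on Day 1 (2 or 1), with every dose through day d given in hospital.

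Days lost = 7 − d. Doses left = 10 − [f + 2(d − 1)].

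| Discharge day | Days covered of 7 | Days lost | Doses left (f = 2 / f = 1) |
|---|---|---|---|
| 2 | 2 | 5 | 6 / 7 |
| 3 | 3 | 4 | 4 / 5 |
| 4 | 4 | 3 | 2 / 3 |
| 5 | 5 | 2 | 0 / 1 |

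For discharges on Days 2 to 4 the all-cause window closes before dosing ends. For Day 5 it closes before the 48 hours have passed.

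**3. What is still captured after discharge, whatever the attribution.** Deaths and readmissions (6.3.1; SAP Appendices B and C), emergency visits, and the listed safety outcomes, which SAP Appendix B follows in all locations to Study Day 29. Removing these, and events judged related, leaves two kinds of event between discharge and Day 7:

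- A serious event judged unrelated and on no list. An example is a pulmonary embolism diagnosed after discharge: 6.2 records it only up to discharge.
- A readmission judged unrelated. It enters the data as a yes/no variable (SAP Appendix C), but no text says it is classified as an SAE.

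**4. Between-arm effect, illustration only.** Assume the same constant daily rate of such events in both arms, in and out of hospital. Let a share p of an arm leave on day d and the rest stay past Day 7. Mean window = 7(1 − p) + d·p. These shares are assumptions. The only discharge figure in the protocol is a planning value of 60.8% discharged at Day 15, borrowed from another trial (7.1), and it says nothing about Days 1 to 7.

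- Day 3, 30% in both arms: 4.9 + 0.9 = 5.8 days each; ratio 1.00.
- Day 3, placebo 30%, hydroxychloroquine 50%: 5.8 against 3.5 + 1.5 = 5.0 days; apparent ratio 5.0/5.8 = 0.86.
- Day 5, placebo 30%, hydroxychloroquine 50%: 4.9 + 1.5 = 6.4 against 3.5 + 2.5 = 6.0 days; apparent ratio 6.0/6.4 = 0.94.

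With equal discharge timing there is under-counting and no distortion. The ratios apply only to the residual events in step 3. They would be closer to 1 if patients well enough to leave have a lower event rate.

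**The case against.** The strongest reply is that the SAE log is a residual channel here. Protocol 11.2 and Appendix C.3 exempt study-specific outcomes, including death and organ failure, from adverse event reporting even in hospital unless they are related or of uncertain relationship. Those outcomes are collected systematically instead. The planned safety comparisons (SAP 7.5) use the listed outcomes to Day 29, and adverse events are presented only descriptively. Related events stay reportable after discharge, with a 24-hour alert when serious, and unanticipated problems carry a 24-hour duty too.

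All of that stands. A reader might infer that SAE reporting simply stops at discharge, or that patients who leave early drop out of safety observation. The documents support neither: only collection regardless of cause ends, and the Day 8, 15 and 29 calls continue. A reader might also infer that SAE rates cannot be compared between arms. That follows only if discharge timing differs, which the documents do not show.

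The reply does not close the gap in step 3. All-cause collection exists to catch serious events that nobody listed or attributed to the drug. The calls ask about adverse events, but no rule says what becomes of an answer judged unrelated.

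**Conclusion.** The point holds in a limited form. Sections 11.2 and 11.3 end all-cause collection at the earlier of Study Day 7 and discharge. That defeats the 48-hour basis for anyone discharged before Day 7, disables the re-hospitalization criterion for events judged unrelated, and conflicts with 6.3.1 and Appendix A.

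The loss per patient is 7 − d days of all-cause collection, for example 5 days after a Day 2 discharge. It affects only SAEs judged unrelated that are neither deaths nor listed outcomes. Its total size cannot be computed, because the documents give neither discharge timing within the first week nor an SAE rate. Against a full seven-day window the frequencies in SAP 7.6 are under-counted; distortion between arms is conditional, and the 0.86 to 1.00 range above rests wholly on assumed discharge shares. The primary efficacy analysis is unaffected.

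**What to change.** - **11.3:** collect SAEs of any cause through Study Day 7 for every patient, discharged or not.
- **11.2:** keep the daily determination for inpatients only. Simply deleting the discharge clause would impose a daily check on patients at home. For patients discharged before Day 7, ascertain SAEs through Day 7 retrospectively at the existing Day 8 call.
- **Classification:** state that SAEs and readmissions with onset by Day 7 that are learned at that call are entered on the adverse event form and classified as SAEs.
- **Reconciliation:** align 11.2 and 11.3 with 6.3.1 and Appendix A, so that sites know which events heard at the Day 8, 15 and 29 calls are entered. SAP 7.6 can then name one fixed window for both arms.

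The cost is a protocol wording change and a little extra site work on adverse event forms; the call and its questions on adverse events and readmissions already exist. The drawback is that telephone recall is less detailed than inpatient review. The Day 8 call may take place as late as Day 14, so recall after a Day 2 discharge could reach back 14 − 2 = 12 days.
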